Following completion of informed consent procedures, subjects will enter the Screening phase of the study.

Two Screening visits are planned to allow most screening procedures to be completed and reviewed during the first visit before lumbar puncture to collect CSF is performed during Screening Visit 2.

Once eligibility is confirmed and before the first dose of study drug, subjects will be randomly assigned on 1:1 basis to placebo or neflamapimod treatment. Investigators and subjects will be blinded to the treatment assignment.

Dosing will start on Day 1 following completion of all Baseline procedures.

During the treatment period, subjects will return to the clinic on Days 21, 42, 84, 126, and 168. Telephone contacts will be conducted to determine subject status and assess compliance between Days 42 and 84 (Visits 5 and 6); Days 84 to 126 (Visits 6 and 7); and Days 126 and 168 (Visits 7 and 8).

Episodic memory and other cognitive assessments will be performed at Baseline and Days 42, 84, and 168.

Lumbar puncture will be performed, and CSF collected at Screening Visit 2 and on Day 168.

A Follow-up visit will be conducted 14 (± 3) days following the last dose of study drug.

TABLE OF CONTENTS

SPONSOR PROTOCOL APPROVAL PAGE	2
INVESTIGATOR’S SIGNATURE OF AGREEMENT PAGE	3
SPONSOR CONTACT INFORMATION	4
SYNOPSIS	5
TABLE OF CONTENTS	9
LIST OF TABLES	12
LIST OF ABBREVIATIONS	13
1. INTRODUCTION	15
1.1. Scientific Rationale	15
1.2. Pre-Clinical Pharmacology Results	16
1.3. Prior Clinical Experience	16
2. OBJECTIVES	20
2.1. Primary Objective	20
2.2. Secondary Objectives	20
3. INVESTIGATIONAL PLAN	21
3.1. Overall Study Design and Plan	21
3.1.1. Screening.....	21
3.1.2. Treatment Period	21
3.1.3. Follow Up.....	21
3.1.4. Early Discontinuation.....	21
3.2. Discussion of Study Design	21
3.2.1. Rationale for Dose Selection	22
4. SELECTION OF STUDY POPULATION	24
4.1. Inclusion Criteria	24
4.2. Exclusion Criteria	24
4.3. Removal of Subjects from Treatment	25
5. TREATMENTS ADMINISTERED	27
5.1. Packaging and Labeling	27
5.2. Study Drug Supply, Storage, and Handling	27
5.3. Drug Accountability, Disposal, Return, or Retention of Unused Study Drug	27
5.4. Method of Assigning Subjects to Treatment Group	28
5.5. Study Blinding and Breaking the Blind	28

5.6.	Dose Modification for Toxicity	28
5.7.	Prior and Concomitant Therapy	28
5.8.	Contraception and Pregnancy	30
5.9.	Activity Restrictions	31
5.10.	Treatment Compliance.....	31
6.	STUDY ASSESSMENTS AND PROCEDURES	32

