### 4 SAMPLE SIZE

Up to 76 subjects per treatment arm (152 total) provides 90% power to detect ES of 0.53 and 80% power to detect ES of 0.46. This level of ES is the minimum treatment effect amount considered clinically relevant and is less than the effect size seen in the Phase 2a studies.

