### 6.2.2 Baseline and Change from Baseline

Baseline is defined as the last non-missing value (either scheduled, unscheduled or repeat) before the subject receives first dose of study drug (Day 1). Visit 3 (Day 1) date is defined as the date of the first dose.

Baseline score of MMSE for each subject is calculated using the average of Screen and Day 1 measurements.

Change from baseline  $CHG = AVAL - BASE$  where  $AVAL$  is the post-baseline value,  $BASE$  is the baseline value.

Baseline z-score will be used as a covariate in the MMRM and ANCOVA analysis. It will be calculated as below:

For baseline total recall, a z-score for each subject is defined by  $z = (x - m) / s$  where  $x$  is the subject's total recall at baseline, and  $m$  and  $s$  are the overall mean and overall standard deviation of total recall at baseline across all subjects. Similarly, a baseline z-score for each subject for delayed recall can be calculated.

A composite baseline z-score for each subject is calculated using equal weighting in the following way:

$Z = 0.5 * z\text{-score for total recall at baseline} + 0.5 * z\text{-score for delayed recall at baseline}$ .

The calculation method can be referenced to [Section 6.2.12](#).

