#### **6.2.12 Z-Score**

For post-baseline total recall, a z-score for each subject at a specific visit is defined by  $z=(x-m)/s$  where  $x$  is the subject's total recall at that visit, and  $m$  and  $s$  are the overall mean and overall standard deviation of total recall from baseline visit across all subjects. Similarly, a z-score for each subject for delayed recall can be calculated.

A post-baseline composite z-score for each subject on the HVLT-R at that visit is calculated using equal weighting in the following way:  $Z = 0.5 * z\text{-score for total recall} + 0.5 * z\text{-score for delayed recall}$ .

Combined change in z-scores =  $Z(\text{post-baseline}) - Z(\text{baseline})$ .

$Z(\text{baseline})$  is described in [Section 6.2.2](#).

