## 6.10 Efficacy Analyses

All efficacy analyses will be based on the Evaluable Efficacy Population by randomized treatment regardless of the treatment actually received. Descriptive statistics by treatment group

and visit will be reported for all efficacy endpoints. All statistical tests will be performed using a two-tailed 5% overall significance level, unless otherwise stated. All comparisons between treatments will be reported with 95% confidence intervals for the difference.

There will be no imputation of missing efficacy data.

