### 6.10.1 Primary Endpoint

The primary efficacy endpoint is:

Combined change in z-scores of total recall and delayed recall on the HVLT-R in neflamapimod-treated subjects compared to placebo-recipients at Week 24.

Neflamapimod 40 mg group will be compared to the placebo group.

The hypothesis test is as follows:

H0:  $\mu_{\text{neflamapimod}} = \mu_{\text{placebo}}$

H1:  $\mu_{\text{neflamapimod}} \neq \mu_{\text{placebo}}$

The null hypothesis will be rejected at a significance level of  $\alpha$  (two-sided) = 0.05. There will be no p-value adjustment for multiplicity.

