### 6.10.2 Primary Efficacy Analysis

The primary endpoint will be analyzed using Mixed Model for Repeated Measures (MMRM) with fixed effects for treatment, background AD-specific therapy (cholinesterase inhibitor or memantine versus no cholinesterase inhibitor or memantine), CDR-Global Score of 0.5 versus 1.0, scheduled visit (nominal) and scheduled visit by treatment interaction, random effect for subject and baseline z-score as a covariate. Least-square means (LSM) and 2-sided 95% confidence intervals (CI) will be provided for treatment group differences and estimated endpoint values by visit.

The normally-distributed assumption for the combined change in z-scores of total recall and delayed recall on the HVLT-R will be examined (at 0.05 alpha level). In case the assumption is violated, rank transformed data will be applied to the MMRM model. Ranks will be determined separately within each time point, based on observed data only.

In addition, Scale plot will be provided for combined change in z-scores of total recall and delayed recall on the HVLT-R at each post-baseline visit by treatment group.

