#### 6.10.4 Secondary Analyses

The secondary efficacy endpoints at Week 24 and follow-up when applicable are:

- Change in WMS immediate and delayed recall composites in neflamapimod-treated subjects compared to placebo-recipients.
- Change in CDR-SB in neflamapimod-treated subjects compared to placebo-recipients.
- Change in MMSE in neflamapimod-treated subjects compared to placebo-recipients.
- Change in CSF biomarkers (T-tau, P-tau181, A $\beta$ 1-40, A $\beta$ 1-42, neurogranin, neurofilament light chain) in neflamapimod-treated subjects compared to placebo-recipients at the end of treatment.

The same method used for the primary efficacy analysis will be applied for the analyses of the change in WMS and change in CDR-SB.

Changes in MMSE and CSF biomarkers will be compared using an analysis of covariance (ANCOVA) with treatment group, background AD-specific therapy, CDR-Global Score as main effects and the baseline assessment as the covariate. The results of the ANCOVA will be summarized using the treatment groups' least square means, the difference between the treatment groups' least square means, the 95% confidence interval for the treatment group difference and the p-value. Scale Plots of Mini-Mental State Examination (MMSE) Score by Visit and by Treatment; and Baseline and Change from Baseline to Day 84 MMSE Score.

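### The primary MMRM holds the baseline slope constant across visits; a baseline-by-visit term would protect the Week 24 comparison at almost no cost

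*SAP*

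**What the plan says.** SAP 6.10.2 crosses visit with treatment but enters baseline once: "scheduled visit (nominal) and scheduled visit by treatment interaction, random effect for subject and baseline z-score as a covariate". SAP 6.2.2 adds nothing further: "Baseline z-score will be used as a covariate in the MMRM and ANCOVA analysis". The response is the composite z-score at the visit minus the composite at baseline (SAP 6.2.12).

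The Protocol synopsis sets three post-baseline HVLT-R visits: "Episodic memory and other cognitive assessments will be performed at Baseline and Days 42, 84, and 168". The hypothesis in SAP 6.10.1 concerns one of them, the comparison "on the HVLT-R in neflamapimod-treated subjects compared to placebo-recipients at Week 24". SAP 6.10 rules out imputing missing efficacy data.

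SAP 6.10.3 plans a sensitivity ANCOVA at Week 24, with the baseline z-score as covariate. SAP 6.10.4 carries the primary model to two secondary endpoints: "The same method used for the primary efficacy analysis will be applied for the analyses of the change in WMS and change in CDR-SB".

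**The concern.** With change as the response, the slope on baseline at a given visit is (correlation of that visit with baseline) × (SD at the visit ÷ SD at baseline) − 1. One common slope is right only if that quantity is the same at Days 42, 84 and 168. If the correlation with baseline weakens over 24 weeks and the spread does not grow to offset it, the Week 24 slope is steeper than the common one.

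Two things could then follow. Chance baseline imbalance would be only partly removed at Week 24, which costs some precision. In addition, the model alone accounts for missing Week 24 scores, so if the subjects lost differ in baseline between the arms, it would correct for that difference with the wrong slope. The primary estimate could then move even though dropout is missing at random given baseline.

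**Working it through.** **Inputs from the documents.** 76 per arm, 1:1 allocation, two-sided 5%, effect sizes 0.53 and 0.46 (SAP 4, 5, 6.10); three post-baseline HVLT-R visits; no imputation.

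**Inputs assumed, because the documents give none.** Correlation of baseline with Days 42/84/168: mild 0.70/0.68/0.62, moderate 0.75/0.70/0.60, strong 0.80/0.70/0.50. Composite SD 0.92 at every visit. Base dropout by Week 24 of 10, 20 or 30%. Where dropout depends on baseline, log-odds of 1 per baseline SD in each interval. No true treatment effect.

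**1. The plan's own figure.** Power = Φ(ES × √(76/2) − 1.96), with √38 = 6.164.
- ES 0.53: Φ(3.267 − 1.96) = 90.4%.
- ES 0.46: Φ(2.836 − 1.96) = 80.9%.

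Both stated powers are reproduced.

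**2. Size of the slope error.** With equal SDs the slope is correlation − 1. In the moderate case the slopes are −0.25, −0.30 and −0.40, and the fitted common slope was about −0.29 to −0.31. Week 24 is therefore under-adjusted by about 0.1 z per 1 z of baseline imbalance. The SD of chance imbalance is 0.92 × √(2/76) = 0.149 z, so the typical conditional error is 0.1 × 0.149 = 0.015 z, averaging to zero over randomisations.

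**3. Precision.** Empirical SD of the Week 24 difference at N = 152 (400 replicates), dropout unrelated to baseline, common slope against by-visit slopes:
- mild: 0.120 against 0.120;
- moderate: 0.135 against 0.134;
- strong: 0.150 against 0.146 (random intercept), 0.153 against 0.147 (unstructured covariance).

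The loss is 0 to 4%. A second simulation at 76 per arm used unit variances and correlations of 0.80/0.78/0.72, 0.80/0.75/0.65 and 0.85/0.75/0.60. Its Week 24 residual variance ratios were 1.01, 1.03 and 1.08; their square roots are 1.005, 1.015 and 1.039, which agrees.

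**4. Shift from dropout.** Large-sample runs (N = 400,000), 20% base dropout, shift removed by the baseline-by-visit term:

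| Dropout and baseline | Mild | Moderate | Strong |
|---|---|---|---|
| Unrelated, or related equally in both arms | ≤0.001 | ≤0.001 | ≤0.001 |
| Related in one arm only, random intercept | 0.013 | 0.023 | 0.045 |
| Related in one arm only, unstructured | 0.013 | 0.025 | 0.056 |
| Opposite directions in the two arms, random intercept | 0.027 | 0.047 | 0.093 |
| Opposite directions in the two arms, unstructured | 0.027 | 0.052 | 0.114 |

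A hand check for the strong one-arm case: the baseline difference among subjects observed at Week 24 was 0.214 z and the unstructured common slope was −0.238, against a true −0.50. Then 0.214 × (0.50 − 0.238) = 0.056, as simulated. The largest setting tried (opposite directions, 30%, strong) gave 0.13 to 0.16 z. The second simulation, with about 15% dropout on active (more often low baseline) and 10–11% on placebo, gave shifts of 0.007 to 0.044 z.

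With the by-visit term the estimate was within about 0.006 z of the truth in every large-sample scenario.

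**5. What a moderate shift would mean.** SD of change at Week 24 is 0.92 × √(2 × 0.40) = 0.82, so 0.025 z is about 0.03 SD. If it ran against the drug, ES 0.53 would act as 0.50 and power would be Φ(3.082 − 1.96) = 87%; ES 0.46 would act as 0.43, giving Φ(2.651 − 1.96) = 76%.

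**The case against.** A common baseline slope is a legitimate prespecified choice in a randomised trial, and much of the case against concern stands.

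- **The slope may not change.** Falling correlation alone does not prove it. If correlation falls from 0.80 to 0.72 while the SD grows by 0.80 ÷ 0.72 = 1.11, the slope is unchanged. SAP 6.2.12 scales every visit by the baseline SD, so the spread is free to grow. Protocol 3.2 describes the HVLT-R as reliable and stable over the short term. That does not settle 24 weeks, but it gives no support to a steep fall.
- **The tempting stronger reading fails.** A reader might infer that the Week 24 result is under-adjusted for certain, or is biased whenever dropout depends on baseline. Neither follows. The first needs a changing slope; the second also needs dependence that differs by arm, since equal dependence cancels. The documents report neither.
- **A check exists.** The Week 24 ANCOVA estimates its own slope and stayed within about 0.007 z of the truth in the large-sample scenarios. A material slope effect would tend to show as disagreement with the MMRM. However, the primary p-value comes from the MMRM, the SAP gives no rule for when the two differ, and SAP 6.10.3 covers only the HVLT-R composite.
- **The simulations simplify.** They omit the strata and do not model the assignment of early-termination scores to the next scheduled visit (SAP 6.2.16) or the replacement of withdrawals before Day 21 (Protocol 4.3). CDR-Global may carry some of the baseline information, and early-termination scores may fill some Week 24 gaps. The shifts are illustrations, not forecasts.

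SAP 6.10.2 names only a random subject effect, so both covariance structures were tried; the choice does not remove the shift.

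**Conclusion.** The point holds in conditional form. The model as written fits one baseline slope for three visits while inference is at the last. If the slope changes by visit, the cost is about 0 to 4% in standard error, with no average bias when dropout is unrelated to baseline or related equally in both arms. If baseline-related dropout also differs between arms, the Week 24 difference shifts by about 0.01 to 0.06 z under 10 to 20% dropout related to baseline mainly or only in one arm, and by more only in extreme settings. The direction depends on which arm loses which subjects.

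All these sizes rest on assumed correlations, SDs and dropout. The documents do not show that the planned estimate is biased. The case for change is that the protection costs almost nothing, which makes this a minor improvement to the model.

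**What to change.** In SAP 6.10.2, add an interaction of baseline z-score with scheduled visit to the fixed effects, and repeat it in SAP 6.2.2 where the covariate is described. With three post-baseline visits this adds two parameters.

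In SAP 6.10.4, state the corresponding term for each endpoint that borrows the model, using that endpoint's own baseline:
- WMS by visit: two extra parameters.
- CDR-SB by visit: one, because Protocol 6.2.6 and Table 6-1 give only two post-baseline assessments, at Visits 6 and 8.

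Keep the Week 24 ANCOVA as planned. No new data are needed and the sample size is unaffected. Make the change before unblinding, so that it cannot look data-driven.

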### 5 RANDOMIZATION

Randomization was stratified by 1) background AD-specific therapy (cholinesterase inhibitor or memantine versus no cholinesterase inhibitor or memantine); and 2) CDR-Global Score of 0.5 versus 1.0.

Eligible subjects were randomized 1:1 to two treatment arms: Neflamapimod 40mg or placebo utilizing a central Interactive Web Response System (IWRS).

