### **6.2.11 HVLT-R and WMS**

The HVLT-R is a verbal learning and memory test, with 6 validated alternate forms. Each form contains 12 nouns, 4 words each from 1 of 3 semantic categories (e.g., precious gems, articles of clothing, vegetables), to be learned, and repeated back to the evaluator over the course of 3 learning trials. Approximately 20–25 minutes later, a delayed recall trial and a recognition trial are completed. The delayed recall requires free recall of any words remembered. The recognition trial is composed of 24 words, including the 12 target words and 12 false-positives, 6 semantically related, and 6 semantically unrelated. The 3 learning trials are combined to calculate a total recall score; the delayed recall trial creates the delayed recall score.

For WMS, LM I & II & II-(Recognition), VPA I & II & II-(Recognition), and VR I & II & II-(Recognition) will be applied.

There are following tests in WMS: Logical Memory test, in which subject is read a story; Verbal-Paired Associates, in which subject is given pairs of words and asked remember which words go together; and Visual Reproduction, in which subject is given drawings of specific shapes. Subjects were then asked to recall the information within each test both in an immediate (WMS-Immediate Recall composite) and delayed (WMS-Delayed Recall composite) basis.

The WMS immediate recall composite score is the total of all of the immediate recall tasks combined and the delayed recall composite is the delayed recall tasks combined.

The HVLT-R and WMS tests must be performed sequentially within the day; with the HVLT-R to be conducted first and completed (including delayed recall component), prior to commencing WMS test.

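### The primary HVLT-R model leaves out the baseline WMS recall score taken the same day; adding it is a small gain in precision at almost no cost, not the repair of an error

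*SAP*

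**What the plan says.** SAP 6.10.2 specifies an MMRM for the combined HVLT-R change, with treatment, the two stratification factors (background AD therapy, CDR-Global 0.5 or 1.0), nominal visit, the interaction of visit with treatment, and a "random effect for subject and baseline z-score as a covariate". SAP 6.2.2 builds that baseline z-score from HVLT-R total and delayed recall only, equally weighted. The sensitivity ANCOVA in SAP 6.10.3 uses the same covariate.

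Protocol Table 6-1 schedules HVLT-R and WMS together on Day 1, where all procedures precede the first dose. Neither test is scheduled at screening. SAP 6.2.11 adds: "The HVLT-R and WMS tests must be performed sequentially within the day". Protocol 1.3 describes both instruments as tests of the recall component of episodic memory. In SAP 6.10.4 and 6.10.5 WMS is an outcome only; no HVLT-R model uses its baseline value.

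For sample size, SAP 4 states "Up to 76 subjects per treatment arm (152 total"), which "provides 90% power to detect ES of 0.53 and 80% power to detect ES of 0.46".

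**The concern.** One sitting of a memory test measures memory with error. Adjusting for it removes only part of the between-subject variation in Week 24 recall, and what remains sets the standard error of the treatment difference. A second pre-dose measure of the same ability can remove some of the remainder. Here it is already scheduled for every subject, so the precision needs only to be specified in advance. The enrolment figure is an upper limit and SAP 4 states no dropout allowance, so a small gain is worth having. What is at stake is the width of the primary confidence interval and a little power. The validity of the test is not in question.

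**Working it through.** **1. Inputs.** 76 per arm and ES 0.46 and 0.53 (SAP 4); 1:1 allocation (SAP 5: "Eligible subjects were randomized 1:1 to two treatment arms"); two-sided 5% (SAP 6.10: "All statistical tests will be performed using a two-tailed 5% overall significance level, unless otherwise stated"). The documents give no HVLT-R or WMS correlation, so those below are assumptions.

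**2. The plan's own figure.** Two-sample noncentral t, 150 degrees of freedom, noncentrality ES × √(76/2):
- ES 0.46: 0.46 × 6.164 = 2.836, power 80.4%
- ES 0.53: 0.53 × 6.164 = 3.267, power 90.1%

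The stated 80% and 90% reproduce.

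**3. Formula for the gain.** Let r1 be the correlation of baseline with Week 24 HVLT-R, r2 that of baseline WMS with Week 24 HVLT-R, and r12 that of the two baselines. Adding WMS cuts the residual variance by the fraction

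c = (r2 − r1·r12)² / [(1 − r1²)(1 − r12²)].

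The interval narrows by 1 − √(1 − c). If the stated ES is on the SD left after HVLT-R adjustment, it becomes ES/√(1 − c). This treats Week 24 as a single complete comparison and ignores the strata.

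**4. Results over assumed correlations.**

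| r1 | r2 | r12 | variance cut c | interval narrower by | power at ES 0.46 |
|---|---|---|---|---|---|
| 0.81 | 0.56 | 0.69 | 0.0% | 0.0% | 80.4% |
| 0.81 | 0.43 | 0.48 | 0.6% | 0.3% | 80.7% |
| 0.80 | 0.40 | 0.40 | 2.1% | 1.1% | 81.3% |
| 0.59 | 0.43 | 0.48 | 4.3% | 2.2% | 82.1% |
| 0.81 | 0.66 | 0.69 | 5.7% | 2.9% | 82.7% |
| 0.70 | 0.50 | 0.50 | 5.9% | 3.0% | 82.7% |
| 0.70 | 0.60 | 0.60 | 9.9% | 5.1% | 84.3% |
| 0.65 | 0.60 | 0.58 | 13.0% | 6.7% | 85.5% |

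Worked example, sixth row: r2 − r1·r12 = 0.50 − 0.35 = 0.15, so c = 0.0225 / (0.51 × 0.75) = 0.059.

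A larger cut needs WMS to predict Week 24 HVLT-R as well as HVLT-R predicts itself (0.70 for all three gives 17%). I do not treat that as plausible.

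**5. Middle cases.** For c of 2% to 7%, the interval narrows by 1.0% to 3.6% and power is 81.2% to 83.2%. In subjects, 152/(1 − c) − 152 is about 3 to 11 in total.

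**6. If the ES is on the raw-score SD.** With r1 = 0.7, HVLT-R adjustment alone makes the ES 0.46/√0.51 = 0.644, with power 97.6%. WMS with r2 = r12 = 0.5 or 0.6 raises this to 98.2% or 98.6%, a gain of one point or less. At r1 = 0.6 and r2 = r12 = 0.5 it moves from 94.1% to 95.7%. The interval still narrows as in step 4.

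**7. The one hint on r1.** Protocol 1.3 reports HVLT-R total recall of 19.1 (±1.5) rising to 22.6 (±2.1), p = 0.015, n = 8. Reading ± as a standard error gives 3.5/√(8 × (1.5² + 2.1²)/2) = 0.68, against 0.69 in the protocol's table, so the reading fits. If the p-value is from a two-sided paired t-test (the protocol does not name the test), t = 3.20, the standard error of the change is 3.5/3.20 = 1.09, and r1 = (1.5² + 2.1² − 1.09²)/(2 × 1.5 × 2.1) = 0.87. Delayed recall gives 0.75 in the same way; one-sided readings give 0.79 and 0.55. With eight subjects this is very uncertain. At r1 = 0.87 and r2 = r12 = 0.5, the power gain is about one point.

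**The case against.** The model is conventional: it adjusts for both stratification factors and the outcome's own baseline. Nothing in the documents makes it biased, inflates type I error or misses the power target. That stands. A reader might infer that the primary analysis is deficient or underpowered; step 2 shows that it is not.

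The size of the gain is assumed, and several features point to the lower part of the range. Protocol 3.2 claims high test-retest reliability for HVLT-R. The baseline score already averages a three-trial total with delayed recall. Because both tests fall on one day, a bad day affects both: at r1 = 0.70 and r2 = 0.55, raising r12 from 0.58 to 0.68 shrinks the cut from 6.1% to 2.0%. CDR-Global may absorb some of what WMS would explain, and WMS includes a visual component. All of this stands, and it is why the range starts at zero.

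Two further inferences should be resisted. The first is that MMSE sets a precedent, because SAP 6.2.2 says "Baseline score of MMSE for each subject is calculated using the average of Screen and Day 1 measurements". It does not: MMSE is scheduled at both visits, whereas HVLT-R is scheduled before dosing only on Day 1, and averaging one test with itself is different from adjusting one instrument by another. The second is that chance imbalance in true memory is a separate harm. Under randomisation the planned interval already allows for it.

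The addition also touches other sections: SAP 6.10 rules out imputing missing efficacy data, and SAP 6.10.4 carries the primary method over to WMS and CDR-SB. These points shape the fix but do not defeat it.

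**Conclusion.** The point holds as an optional gain in efficiency. The documents confirm that baseline WMS recall is collected before dosing, on the same day, and is unused in the HVLT-R models. Pre-specifying it does not compromise type I error. The expected benefit is modest: a 0-13% cut in residual variance, about 2-7% in middle cases, hence an interval about 1-4% narrower. Power at ES 0.46 moves from about 80% to 81-83% only if that ES is on the HVLT-R-adjusted SD, which SAP 4 does not say. On the raw SD, with r1 of 0.7 or more, the power gain is one point or less. All of these figures rest on assumed correlations.

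**What to change.** Before unblinding:
- **SAP 6.10.2 and 6.10.3:** add the baseline WMS immediate plus delayed recall score (the 0-228 score of Table 14.2.2.3) as a second continuous covariate in the HVLT-R MMRM and ANCOVA, and keep the baseline z-score. Say how it enters if the rank-transform fallback is used.
- **SAP 6.10.4:** state that this term is not added to the WMS model, which already has its own baseline, and say whether the CDR-SB model carries it.
- **SAP 6.10:** state that a missing baseline WMS is replaced by the overall mean so that no subject is lost, and that this is covariate handling and not imputation of efficacy outcomes.

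The cost is a few sentences of SAP text and no new data. If WMS adds nothing beyond HVLT-R, the loss is about one degree of freedom.
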